Participants in both conditions will be asked to complete an identical pre-test questionnaire. The questionnaire will be sent to via email or postal mail, and/or will be scheduled to be completed over the phone. We will ask about the participant's background, caregiving role, and comfort speaking with health care providers. It will take approximately 15-20 minutes to complete.

Intervention condition. Participants in the intervention condition will be contacted by a member of the study team to start the PICT workbook. The PICT workbook consists of four sessions and will be completed over the telephone with a study team member. Sessions are conducted once a week and last approximately 30-60 minutes each. Participants will also be asked to read sections of the PICT workbook and complete exercises between sessions. The reading and exercises will take 10-15 minutes to complete. After the final session of the intervention, a study team member will contact the participant by telephone to complete another set of questionnaires (at 12 weeks after the pre-test questionnaire). The questionnaire will be sent to via email, postal mail, or will be scheduled to be completed over the phone. The post-test questionnaires will take approximately 20 minutes to complete and will ask about the participant's comfort and confidence in communicating with health care providers, behaviors he or she observes in the recipient, and views of the PICT workbook. Participants will also be asked to participate in a 20-30 minute telephone interview to elaborate their responses to the questionnaire. Participants must agree to be audiotaped to participate in the study.

Control condition. Caregivers in the control condition will receive an informational pamphlet about pain in dementia and a link to the Alzheimer's Association website. Twelve weeks after the participant completes the pre-test questionnaire, she or he will be contacted by a member of the study team to complete the post-test questionnaire. The questionnaires will be sent via email, postal mail, or will be scheduled to be completed over the phone and will take approximately 20 minutes to complete.

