3.2 Interviews, Focus Groups, Surveys, and/or Observations

A. Administration

- *Timing and Frequency*
 - Interview and field-testing phases: Caregiver and healthcare professional subjects will complete a one-time 20-30 minute interview accompanied by a brief questionnaire. Interviews will be conducted by a research nurse or trained co-investigators.
 - Pilot testing phase: PICT will consist of 4 weekly 30-60-minute sessions delivered by a study team member. In between sessions, participants will have 10-15 minutes of reading and exercises to complete.
- *Location*

Interview and field testing phases will take place in-person in private offices at WCMC/NYP or over the telephone. The participant, in special circumstances (e.g. scheduling issues) may opt to have the interview take place in a private location convenient to them.

Pilot testing will take place over the telephone.
- *Procedures For Audio And Visual Recording*

All interviews will be recorded and transcribed by a certified, secure, and WCM-approved transcription agency.
- *Person Identifiers*

Co-investigators may review EPIC to identify potential participants who meet eligibility. Contact information and appointment information will also be collected for either in-person or letter (postal and email) recruitment. Only data from potential participants will be stored on secure servers. These data will be deleted upon completion of the study or immediately if a patient chooses not to participate in the study.

B. Study Instruments

Interview Phase 1

- Caregiver subjects
 - Screening questions
 - Caregiving questions
 - Brief cognitive screener (BOMC)
 - Brief Questionnaire – Caregiver
 - Demographics
 - Caregiving Questions
 - Patient Health Characteristics
 - Interview Guide – Caregiver
 - Field test questions - Caregiver
- Healthcare Professional subjects
 - Brief Questionnaire – Provider
 - Demographics
 - Medical practice questions
 - Interview Guide – Provider
 - Field test question – Provider

Pilot Test Phase

- Caregiver subjects in PICT (intervention) group
 - Pre-test Questions for All Caregiver Participants
 - Post-test Questions for Caregivers in PICT Group
 - Exit Interview Questions
- Caregiver subjects in control group
 - Pre-test Questions for All Caregiver Participants
 - Post-test Questions for Caregivers in Control Group

4. Study Design

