4.2 Inclusion Criteria

Family Caregivers:

1. Age 21 or older
2. English speaking
3. Cognitively intact (BOMC ≤ 10)
4. Provides at least 8 hours of care per week to a person with dementia who also has a pain diagnosis
5. Has access to the internet

Healthcare professionals:

1. Currently providing clinical services to persons with dementia and/or chronic pain
2. Has provided these clinical services for at least 1 year

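### Section 3.1 leaves post-test mode and collector open, so PICT caregivers could give self-reported outcomes by phone to the person who delivered their sessions, which could favour PICT

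*Combined protocol and SAP*

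**What the plan says.** **Post-test, PICT arm (Section 3.1, Intervention condition).** At 12 weeks after the pre-test, "a study team member will contact the participant by telephone to complete another set of questionnaires". The next sentence widens the mode: "The questionnaire will be sent to via email, postal mail, or will be scheduled to be completed over the phone". The content covers how comfortable and confident caregivers feel with clinicians, the behaviours they see in the person they care for, and their opinion of the workbook. A 20-30 minute telephone interview to expand on the answers is also requested. Table 2 in Section 6.1 marks this exit interview as intervention-only.

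**Post-test, control arm (Section 3.1, Control condition).** Controls are "contacted by a member of the study team to complete the post-test questionnaire", also at 12 weeks, and "The questionnaires will be sent via email, postal mail, or will be scheduled to be completed over the phone". The contact sentence does not mention the telephone.

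**Pre-test, both arms (Section 3.1).** "The questionnaire will be sent to via email or postal mail, and/or will be scheduled to be completed over the phone".

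**Sessions.** "The PICT workbook consists of four sessions and will be completed over the telephone with a study team member" (Section 3.1). Section 3.2 agrees: "PICT will consist of 4 weekly 30-60-minute sessions delivered by a study team member". The sessions and the PICT post-test contact carry the same generic staff label.

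**Other relevant text.** Section 3.2 A, under Location, places pilot testing on the telephone without exception. Section 3.2 B lists separate post-test forms for the two arms. Inclusion criterion 5 for caregivers (Section 4.2) is "Has access to the internet", and Section 7.1.1 describes REDCap as offering web-based data entry. Section 8 names no model term or sensitivity analysis for mode or collector. The documents contain no statement on masking.

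**The concern.** The questionnaire outcomes are self-ratings by caregivers who know their arm. A caregiver who answers aloud to the person who coached them through four sessions may answer more favourably than on a form completed alone. Controls have no coach, so this courtesy effect can act in one arm only.

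Two results are exposed. Hypothesis 3 compares the arms, and a one-sided shift in the PICT ratings would look like a treatment effect. Hypothesis 2b sets a 70% benchmark on participants' ratings of the intervention; these involve PICT caregivers only, so they could be inflated without any difference in mode between arms.

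The plan does not ask for mode or collector to be recorded, so the effect could not be examined afterwards. A phone interviewer would also learn the arm from the PICT form, because it asks about the workbook.

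**Working it through.** **Step 1: no figure to reproduce.** The documents state no effect size, SD, alpha, power or mode effect. What follows is illustration under stated assumptions.

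**Step 2: what differs between arms.**

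| Item | PICT | Control |
|---|---|---|
| Modes offered at post-test | email, post, phone | email, post, phone |
| Contact sentence | names the telephone | mode not named |
| Extra telephone interview | yes | no |
| Possible contact with own session staff | not excluded | not applicable |
| Rule for choosing mode | none | none |

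**Step 3: two mechanisms to keep apart.**
- *Coach effect.* Answering to session staff shifts a PICT caregiver's rating by b SD. Bias = b × s, where s is the share of PICT caregivers so interviewed. It needs no difference in phone use between arms.
- *General mode effect.* Any phone interview shifts ratings by b SD in either arm. Bias = b × (PICT phone share − control phone share). It is zero when the shares are equal.

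**Step 4: inputs.** From the documents: n = 50 per arm (Section 3.1) and 30 per arm (Section 8). These disagree, so both are used. Assumed: b = 0.2 SD, s = 50% or 100%, true effect zero, two-sided alpha 0.05, simple two-sample comparison of post-test means (not the mixed model of Section 8).

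**Step 5: coach effect.**
Bias: 0.2 × 0.5 = 0.10 SD; 0.2 × 1.0 = 0.20 SD.
Standard error of the difference, in SD units, is √(2/n): √(2/50) = 0.200; √(2/30) = 0.258.
False-positive rate = Φ(bias/SE − 1.96) + Φ(−bias/SE − 1.96).

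| n per arm | s | bias/SE | False-positive rate |
|---|---|---|---|
| 50 | 50% | 0.10/0.200 = 0.50 | 7.9% |
| 50 | 100% | 0.20/0.200 = 1.00 | 17.0% |
| 30 | 50% | 0.10/0.258 = 0.39 | 6.7% |
| 30 | 100% | 0.20/0.258 = 0.77 | 12.1% |

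Nearly all of the excess lies in PICT's favour: at n=50 and s=100%, 16.9 of the 17.0 points.

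**Step 6: general mode effect.** With equal phone shares the bias is 0 and the rate stays at 5.0%. With 80% by phone in PICT and 50% in control, bias = 0.2 × 0.3 = 0.06 SD, and the rate is 6.0% at n=50 and 5.6% at n=30. Mixed mode alone is therefore a minor matter unless uptake differs widely.

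**Step 7: sensitivity to b.** If b is 0.3 SD rather than 0.2, the coach-effect rates at n=50 become 11.7% (s=50%) and 32.3% (s=100%). At n=30 they are 8.9% and 21.3%. With no caregiver interviewed by session staff and equal phone shares, the rate is the nominal 5%.

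**The case against.** The strongest reply is that the plan treats the arms almost alike: both are offered the same three modes in nearly the same words, and equal options add noise, not bias, unless uptake differs. This stands. The telephone wording for PICT and the exit interview make a higher phone share in PICT possible, but they do not establish it. A reader might infer that mode will differ by arm; the documents do not support saying so.

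A reader might also infer that session staff are meant to collect the post-test. No sentence says this. The shared label is generic, and the plan merely fails to rule it out.

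The exit interview is weaker evidence than it looks. Its purpose is to expand on questionnaire answers, which implies that the answers come first. Still, nothing prevents one call from covering both.

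If the Location statement in Section 3.2 governs, everyone answers by phone and mode does not vary. That would remove the mode question but leave the question of who makes the call.

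Finally, the trial tests preliminary efficacy, and retention is part of the feasibility benchmark in Hypothesis 2a. Section 7.2.3 describes an older population, so making the phone a fallback could cost some responses. That is a fair cost, and the fix should allow for it.

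**Conclusion.** The gap is real and worth closing. Mode is unregulated, the collector is neither named nor masked, and a caregiver's own session deliverer is not excluded from taking that caregiver's self-ratings. Under an assumed 0.2 SD shift, the bias is 0.1 to 0.2 SD when 50% to 100% of PICT caregivers answer to session staff. The false-positive rate is then about 8% to 17% at n=50 per arm and 7% to 12% at n=30, against a nominal 5%. The shift and the shares are assumptions; the documents supply neither.

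Two stronger readings should be avoided. One is to express the bias as a fraction of the treatment effect: the plan states no effect size, so any such fraction would be assumption over assumption. The other is to extend the point to the primary variable. Section 8 names a dichotomous one, whether the caregiver gets in touch with the primary care practice, and gives no data source. It is affected only if it is self-reported, and the SD arithmetic above does not apply to it. The point holds for the questionnaire outcomes described in Section 3.1 and for the acceptability ratings.

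**What to change.** In Section 3.1:

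1. Make REDCap self-completion by emailed link the default in both arms, at both pre-test and post-test. Section 8 analyses treatment by time, so a change of mode within a caregiver also matters.
2. Place the outcome items common to both arms before the workbook items and before the exit interview.
3. Use phone or post only after non-response, or where the caregiver cannot complete the form online. Have any post-test call made by an existing team member who did not deliver that caregiver's sessions.
4. Record mode and collector at both time points.

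In Section 8, add a sensitivity analysis by mode. Reconcile the Location statement in Section 3.2 with the email and postal options in Section 3.1.

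The cost is mainly wording and form set-up. Internet access is already required, email is already a permitted mode, and REDCap is already the data system. Self-completion needs no assessor; the back-up call needs a second existing team member, not a new post. The downside is that caregivers who prefer the phone may need a reminder, with a possible small loss of response that would count against the retention benchmark. Bias from caregivers knowing their own arm remains.

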3.2 Interviews, Focus Groups, Surveys, and/or Observations

A. Administration

- *Timing and Frequency*
 - Interview and field-testing phases: Caregiver and healthcare professional subjects will complete a one-time 20-30 minute interview accompanied by a brief questionnaire. Interviews will be conducted by a research nurse or trained co-investigators.
 - Pilot testing phase: PICT will consist of 4 weekly 30-60-minute sessions delivered by a study team member. In between sessions, participants will have 10-15 minutes of reading and exercises to complete.
- *Location*

Interview and field testing phases will take place in-person in private offices at WCMC/NYP or over the telephone. The participant, in special circumstances (e.g. scheduling issues) may opt to have the interview take place in a private location convenient to them.

Pilot testing will take place over the telephone.
- *Procedures For Audio And Visual Recording*

All interviews will be recorded and transcribed by a certified, secure, and WCM-approved transcription agency.
- *Person Identifiers*

Co-investigators may review EPIC to identify potential participants who meet eligibility. Contact information and appointment information will also be collected for either in-person or letter (postal and email) recruitment. Only data from potential participants will be stored on secure servers. These data will be deleted upon completion of the study or immediately if a patient chooses not to participate in the study.

B. Study Instruments

Interview Phase 1

- Caregiver subjects
 - Screening questions
 - Caregiving questions
 - Brief cognitive screener (BOMC)
 - Brief Questionnaire – Caregiver
 - Demographics
 - Caregiving Questions
 - Patient Health Characteristics
 - Interview Guide – Caregiver
 - Field test questions - Caregiver
- Healthcare Professional subjects
 - Brief Questionnaire – Provider
 - Demographics
 - Medical practice questions
 - Interview Guide – Provider
 - Field test question – Provider

Pilot Test Phase

- Caregiver subjects in PICT (intervention) group
 - Pre-test Questions for All Caregiver Participants
 - Post-test Questions for Caregivers in PICT Group
 - Exit Interview Questions
- Caregiver subjects in control group
 - Pre-test Questions for All Caregiver Participants
 - Post-test Questions for Caregivers in Control Group

4. Study Design

4.1 Study Population

Healthy volunteers that are caregivers and healthcare providers of persons with dementia and pain.

4.2 Inclusion Criteria

Family Caregivers:

1. Age 21 or older
2. English speaking
3. Cognitively intact (BOMC ≤ 10)
4. Provides at least 8 hours of care per week to a person with dementia who also has a pain diagnosis
5. Has access to the internet

Healthcare professionals:

1. Currently providing clinical services to persons with dementia and/or chronic pain
2. Has provided these clinical services for at least 1 year

4.3 Exclusion Criteria

Family Caregivers:

1. Paid Caregiver
2. Age 20 or younger
3. Non-English speaking
4. Cognitively impaired
5. Does not provide at least 8 hours of care per week to a person with dementia who also has a pain diagnosis
6. Has provided care < 6 months
7. Currently enrolled in hospice
8. The patient to whom the caregiver provides assistance is enrolled in hospice

Healthcare professionals:

1. Not currently providing clinical services to persons with dementia and/or chronic pain
2. Has provided these clinical services for fewer than 1 year

4.4 Strategies for Recruitment and Retention

Overview of Caregiver Recruitment Procedures

Co-investigators will meet with health care providers who see patients at the Center on Aging, the Alzheimer's Disease and Memory Disorders Program, and Weill Cornell Internal Medical Associates to make them aware of the study protocol, including the plan to send recruitment letters (postal mail or email) to their patients' caregivers. During the meetings, the co-investigators will ask each provider to review his or her patient list and identify individuals who have both pain and dementia, as well as a family caregiver. When meeting with these healthcare providers, co-investigators will verify that the caregiver lives with the patient and/or obtain the caregiver contact information from the providers. Recruitment letters will then be sent by mail or email (when available) to the caregivers of the identified patients. Patients themselves will not be contacted, and every effort will be made to contact the caregiver directly. When possible, letters will be sent to the emergency contact (i.e., caregiver) if their telephone matches that of the patient, or by email. The recruitment letter will describe the study and advise caregivers that they may decline participation by emailing or placing a telephone call to the study team. Approximately 2 weeks after the initial letter (postal mail or email) is sent, caregivers who have not opted out will be telephoned or emailed by the trained co-investigator to confirm their interest.

For caregivers that care for a patient at recruitment sites, patients' medical records will first be reviewed by a trained co-investigator who will confirm whether or not they meet eligibility criteria (dementia and pain diagnosis). Recruitment site caregivers will be approached in the waiting room prior to their doctor's visit. The co-investigator will perform the consenting process either in the waiting room or a private office, if available.

Other caregivers will be recruited via caregiving resources and groups in the community including the WCM/NYP Geriatrics caregiver support groups, local community centers, senior service agencies, etc. Interested individuals will provide their name and contact details on a sign-up sheet.

Trained co-investigators will use the caregivers' preferred method of contact to inform them about the study (phone or email). The procedure outlined above (i.e., co-investigator mails/emails the consent form in advance and requests the signed consent form back prior to conducting the interview) will then be followed. If time allows, co-investigators may choose to have participants consent in-person at recruitment sites, and in that case, they will also be given the first survey to mail back at their convenience after consent is obtained.

Caregivers may also contact the study team to participate after seeing a recruitment flyer. The Guthrie Clinic also has agreed to be a recruitment site. They will be limited to posting and handing out WCM flyers to potential participants.

Additional efforts will rely on making study information available on online platforms. Online platforms may include, but are not limited to: caregiver/dementia interest pages on Facebook, participant registries, online bulletin boards, mobile apps and websites, etc. Methods include, but are not limited to: posting flyers, posting messages describing the project and inviting interested participants to contact study members (see "Social Media Posting" document), including study information in e-newsletters, etc. Permission from group administrators will be received prior to posting on any social media group platform. In addition, ResearchMatch.org will be added as a recruitment method.

Additionally, snowball recruitment method will be used to ask potential participants to share study information with other caregivers who may be interested in the study.

Trained co-investigators will use the caregivers' preferred method of contact to inform them about the study (phone or email). The procedure outlined above (i.e., co-investigator mails/emails the consent form in advance and requests the signed consent form back prior to conducting the interview or REDCap consent) will then be followed.

Interview and field testing phases: Caregiver participants will be compensated \$15 after completing the study interview in the form of a ClinCard.

Pilot testing phase: Participants will be compensated \$10 after completing the pre-test questionnaires and \$30 after completing the post-test questionnaires. Participants in the PICT (intervention) condition will also receive \$10 after each of the 4 sessions. Compensation will be paid in the form of a ClinCard.

Overview of Health Care Provider Recruitment Procedures

Health care providers will be informed of the opportunity to participate in the brief questionnaire and interview during practice site meetings and/or one-on-one conversations about the project.

5. Registration Procedures

5.1 Subject Registration (WCM only)

Subjects will be registered within the WRG-CT as per the standard operating procedure for Subject Registration.

5.2 Subject Registration (Sub-sites)

N/A

6. Study Procedures

6.1 Schedule of Assessments

Table 1. Schedule of trial events for interview and field testing phases

	Pre-study	Visit 1 (Interview)
Screening	X	
Informed Consent	X	X
Demographics and Questionnaire		X
Semi-structured Interview		X

Table 2. Schedule of trial events for the pilot test phase

	Pre-study	Week 1	Week 2	Week 3	Week 4	Post-study
Screening	X					
Informed Consent	X					
Demographics and Pre-test Questions		X				
Weekly Session *		X	X	X	X	
In-home reading *		X	X	X	X	
Post-test Questions						X
Exit Interview *						X

* denotes intervention participants only

7.0 Data Reporting / Regulatory Considerations

7.1 Data Collection

The data collection plan for this study is to utilize REDCap to capture all treatment, toxicity, efficacy, and adverse event data for all enrolled subjects.

7.1.1 REDCap

REDCap (Research Electronic Data Capture) is a free data management software system that is fully supported by the Weill-Cornell Medical Center CTSC. It is a tool for the creation of customized, secure data management systems that include Web-based data-entry forms, reporting tools, and a full array of security features including user and group based privileges, authentication using institution LDAP system, with a full audit trail of data manipulation and export procedures. REDCap is maintained on CTSC-owned servers that are backed up nightly and support encrypted (SSL-based) connections. Nationally, the software is developed, enhanced and supported through a multi-institutional consortium led by the Vanderbilt University CTSA.

